6.2 Other Safety Data Collection

Columbia Suicide Severity Rating Scale (C SSRS)

The C-SSRS reports the severity of both suicidal ideation and behavior. Suicidal ideation is classified on a 5-item scale: 1 (wish to be dead), 2 (nonspecific active suicidal thoughts), 3 (active suicidal ideation with any methods [not plan] without intent to act), 4 (active suicidal ideation with some intent to act, without specific plan), and 5 (active suicidal ideation with specific plan and intent). The C-SSRS also captures information about the intensity of ideation, specifically the frequency, duration, controllability, deterrents, and reasons for the most severe types of ideation. Suicidal behavior is classified on a 5-item scale: 0 (no suicidal behavior), 1 (preparatory acts or behavior), 2 (aborted attempt), 3 (interrupted attempt), and 4 (actual attempt). More than one classification can be selected provided they represent separate episodes. For actual attempts only, the actual or potential lethality is classified for the initial, most lethal, and most recent attempts. Any subject who has suicidal ideation with intent (with or without plan), either via answering "yes" to question 4 and/or question 5 to the suicidal ideation section or "yes" to any question in the suicidal behavior section of the C-SSRS, or via clinical interview, will be evaluated immediately by the investigator and discontinued from the study. The AbbVie medical contact will also be notified. The subject should receive appropriate follow-up as in routine clinical practice. In addition, if the subject expresses suicidal ideation at any time during the study, the

investigator and the AbbVie medical contact should be notified immediately. Under no circumstances should a subject who has positively endorsed or expressed suicidal ideation be left alone, be allowed to exit the site, or go home before a qualified medical professional has evaluated the subject's risk.

The C-SSRS is administered by the clinician or trained personnel via subject interview in person or over the telephone, as applicable, at all study visits. At Visit 1 (screening), the C-SSRS will be completed for the subject's lifetime history and for the 6 months prior to screening. At all other visits the C-SSRS will be completed for ideation and behavior since the previous visit.

7 STATISTICAL METHODS & DETERMINATION OF SAMPLE SIZE

7.1 Statistical and Analytical Plans

The statistical methods provided in this protocol will be focused on primary and key secondary analyses. Complete and specific details of the statistical analysis will be described in the SAP, which must be in place before randomization codes are unmasked for any analysis.

A primary analysis will be performed at the end of the double-blind phase and a final analysis at the end of the open-label phase. A database lock will occur, and randomization data will be released when all subjects have completed the double-blind phase through the Week 24 visit. The planned primary analysis will be performed at that time. The final database will be locked when all subjects have completed the open-label phase of the study. For analysis purposes, subjects who complete the Week 24 visit and remain in the study regardless of whether or not they receive further treatment, will be considered as having entered the open-label phase. The planned final analysis will be performed after the final database is locked. The final analysis will include data from both the double-blind phase and the open-label phase of the study.

7.2 Definition for Analysis Populations

The following analysis populations are defined for this study:

- The intent-to-treat (ITT) population includes all subjects who are randomized. This will be used as the full analysis set (FAS) population. Subjects will be summarized according to their randomization assignment (i.e., as randomized), regardless of study intervention received. (All subjects will have non-missing baseline data for the primary efficacy variable because it is a condition of randomization, and therefore, the ITT population is not being modified with such a constraint.)
- The safety population includes all randomized subjects who have at least 1 study treatment intervention (i.e., BOTOX or placebo). Subjects will be summarized according to the study intervention received (i.e., as treated), regardless of their randomization assignment.

7.3 Handling Potential Intercurrent Events for the Primary and Key Secondary Endpoints

The estimand corresponding to the primary objective of this study is displayed in Section 3.1. Among intercurrent events, it includes study discontinuations, especially if due to lack of efficacy or due to AEs. Also included are any significant protocol deviations that could affect the primary endpoint, such as taking rescue medication or not receiving the Week 12 treatment. A sensitivity analysis will impute scores differently for such intercurrent events (e.g., reversion toward baseline).

The primary analysis assumes that missing data are missing completely at random or missing at random. A sensitivity analysis will use the same model as the primary analysis after imputation of missing data by the modified last observation carried forward (mLOCF) rate-change method, which adjusts the most recent observation by the average change since that observation within the same treatment regimen. An additional sensitivity analysis, which is aimed at intercurrent events, will instead impute missing data by reversion toward baseline for subjects who have intercurrent events that could affect the primary endpoint. These sensitivity analyses will be described in more detail in the SAP.

7.4 Statistical Analyses for Efficacy

The efficacy analyses will be based on the ITT population, in general. Baseline for efficacy analyses is defined as the last non-missing efficacy assessment before randomization. For the primary efficacy variable and similar variables based on headache diary data, baseline will be the count of affected days during the 4 weeks ending the day before randomization.

Summary and Analysis of the Primary Endpoint

The primary efficacy endpoint is defined in Section 3.2. The primary efficacy analysis will test the null hypothesis that BOTOX (each dose group separately) and placebo are equally effective, as measured by the change from baseline in monthly migraine days across Months 5 and 6.

A mixed model repeated measures (MMRM) analysis will be used for the primary analysis, using data for baseline and each month of the double-blind, placebo-controlled phase (i.e., months ending with Weeks 4, 8, 12, 16, 20, and 24).¹⁷ The statistical model will include treatment (BOTOX 195 U, BOTOX 155 U, and placebo), month, country, strata of [REDACTED], and treatment group-by-month interaction as fixed effects, with the baseline number of monthly migraine days as a covariate, included as a continuous variable rather than as the binomial stratification variable. Subject and residual errors will be random effects. The primary comparisons of interest will be the pairwise comparisons of each BOTOX dose (195 U and 155 U) versus placebo across Months 5 and 6.

Each dose comparison will be analyzed across primary and secondary endpoints in the order described in Section 7.7, using a ranked-order serial gatekeeping approach to control the overall type I (false-positive) error rate. For each BOTOX dose versus placebo, each variable/dose pair will be examined for significance only if significance was determined for all variable/dose pairs ranked ahead of it.

The primary analysis assumes that missing data are missing completely at random or missing at random. Details of the sensitivity analyses will be provided in the SAP. A 2-sided test with a P value ≤ 0.05 will be

considered as statistically significant for the treatment group comparisons of each BOTOX dose (195 U and 155 U) versus placebo.

Interaction effects will be examined at the 0.10 level by including treatment group-by-country interaction in a separate expansion of the primary MMRM model. If there is a significant interaction ($P \leq 0.10$) in the expanded MMRM model, the relevant reduced model will be examined for interpretation (i.e., by country).

Secondary analyses of covariance (ANCOVAs) of the primary efficacy variable (monthly migraine days) will be made for each month of the double-blind, placebo-controlled phase (i.e., months ending with Weeks 4, 8, 12, 16, 20, and 24), using the same model as for the primary MMRM analysis, but without repeat measures (i.e., omitting fixed effect of month and treatment group-by-month interaction).

A sensitivity analysis will use the same MMRM model after imputation of missing data by the mLOCF rate-change method, which adjusts the most recent observation by the average change since that observation within the same treatment regimen. This method has been chosen for consistency with methods used for the Phase 3 CM studies of BOTOX. Additional sensitivity analyses, including those using other imputation methods, will be described in the SAP (e.g., reversion toward baseline).

Subgroup Analysis of the Primary Endpoint

The primary effectiveness analysis (MMRM of change in monthly migraine days without the fixed effect of the corresponding subgroup variable) will be repeated for subgroups defined by each randomization stratification subgroup (monthly migraine days at baseline \geq [redacted] [yes/no] and [redacted] [redacted] [yes/no]), for medication overuse subgroup [yes/no] (see Section 8.2 in the Operations Manual), for each gender, and for each country. Additional subgroup analyses will be described in the SAP.

Summary and Analysis of Secondary Endpoints

The secondary efficacy endpoints are defined in Section 3.3; Each dose comparison will be analyzed across primary and secondary endpoints in the order described in Section 7.7, using a ranked-order serial gatekeeping approach to control the overall type I (false-positive) error rate. For each BOTOX dose versus placebo, each variable/dose pair will be examined for significance only if significance was determined for all variable/dose pairs ranked ahead of it.

The comparisons of interest for each of these secondary endpoints will be the pairwise comparisons of each BOTOX dose (195 U and 155 U) versus placebo, with no statistical comparison between the BOTOX doses.

The analysis results of the change from baseline in monthly headache days, MSQ v2.1 RFR domain score, monthly acute headache medication days, and AIM-D Physical Impairment domain score (or HIT-6 score [for Europe]) across Months 5 and 6 will come from the same type of MMRM analysis of observed data used for the primary efficacy endpoint, except that the baseline covariates will be monthly headache days, MSQ v2.1 RFR domain score, monthly acute headache medication days, and AIM-D Physical Impairment domain score (or HIT-6 score [for Europe]), respectively.

Logistic regression will be used to analyze responder variables using the same ANCOVA analysis model described for the primary variable (i.e., the MMRM model used for the primary analysis, but without repeat measures). The proportion of subjects with 50% reduction in the change from baseline in monthly migraine days across Months 5 and 6 will be summarized, along with p-values from the logistic regression. The primary assessment will be the pairwise comparison of each BOTOX dose versus placebo. A sensitivity analysis will use the same logistic model after imputation of missing data for the underlying primary variable by the mLOCF rate-change method, as described above. Alternatively, GLIMMIX models for repeated measures of binary data might be used in place of MMRM models; if so, the methodology will be described in the SAP.

Summary and Analysis of Other Endpoints

The other endpoints are defined in Section 3.4. These endpoints are not planned to be included in the multiplicity control. Hence, results will be considered descriptive and potentially supportive of the results for the primary and secondary endpoints.

The comparisons of interest for each of the other endpoints will be the pairwise comparisons of each BOTOX dose (195 U and 155 U) versus placebo, with no statistical comparison between the BOTOX doses. Specific details of the statistical analysis of other efficacy endpoints will be described in the SAP.

In general, though, for continuous and ordinal variables, the change from baseline analysis will be done with the same type of MMRM or ANCOVA analyses described for the primary efficacy endpoint, except that the baseline covariate will be for the variable being analyzed. For [REDACTED] which is recorded as change score postbaseline, the [REDACTED] baseline score will be used as a surrogate baseline covariate, to adjust for variation in response that is due to baseline differences between treatment groups.

In general, for responder variables, analysis of the responder status will be done with the same methods described for the secondary variable of 50% responder status.

For [REDACTED], the change from baseline analysis will be done with the same type of MMRM or ANCOVA analyses described for the primary efficacy endpoint, except that the model will use [REDACTED]. The counts for a given week will be prorated to 28-day counts before calculating the change from baseline.

The analysis of treatment-related TEAEs (by descending order of PT incidence) will be repeated for subgroups defined by each randomization stratification group (monthly migraine days at baseline \geq [redacted] [yes/no] and [redacted] [yes/no]), for medication overuse subgroup [yes/no] (see Section 8.2 in the Operations Manual), for each gender, and for each country. Additional subgroup analyses will be described in the SAP.

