2.2 Benefits and Risks to Subjects

BOTOX is approved in over 90 countries for the prophylaxis or symptom relief of headaches in adults with CM. The similar disease characteristics, along with the established efficacy of BOTOX in adults with CM, supports the assumption that the benefit/risk profile in EM will be favorable.

The results of the safety analyses of the Phase 3 CM population support the known safety and tolerability profile of BOTOX seen in a large number of other clinical applications, when BOTOX is administered every 12 weeks. Overall, no safety findings emerged from the CM safety database, or from Phase 4 studies and the postmarketing database, that raise concerns over the use of BOTOX at doses of 155 or 195 U administered intramuscularly every 12 weeks in the target population of adults with migraine.

In the Phase 3 CM studies, the most frequently reported adverse drug reactions occurring in $\geq 5\%$ of patients following injection of BOTOX were neck pain reported in 8.7% of patients. Additional adverse drug reactions that were reported in $\geq 2\%$ of BOTOX-treated patients were headache (4.7%), migraine

(3.8%), eyelid ptosis (3.6%), musculoskeletal stiffness (3.6%), muscular weakness (3.5%), injection site pain (3.3%), myalgia (3.1%), musculoskeletal pain (2.6%), and facial paresis (2.2%).

The doses and dosing paradigm confirmed in the Phase 3 CM studies will be utilized in this Phase 3 EM Study, M21-307.

Known risks associated with BOTOX administration are pre-existing neuromuscular disorders, immunogenicity, distant spread of toxin, and dysphagia in chronic migraine patients.

Based on the collective evidence from the Phase 3 CM studies, observational studies, and clinical experience, international consensus guidelines recommend BOTOX as both effective and safe in subjects with CM.⁷⁻⁹ The lack of need for slow dose escalation, the relatively rapid onset of therapeutic benefits, and the positive tolerability of injectable therapies such as BOTOX contribute to a favorable benefit-risk profile.¹⁰

Further details, including findings from completed studies and other safety data, are provided in the current Investigator's Brochure for BOTOX.

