Possible distant spread of toxin (PDSOT) is defined as a possible pharmacologic effect of botulinum toxin at sites noncontiguous and distant from the site of injection. Utilizing a standardized methodology to assess for PDSOT, Medical Dictionary for Regulatory Activities (MedDRA) preferred terms (PTs) that may be associated with botulinum toxin effects have been prospectively identified (see the statistical analysis plan [SAP] for a complete list of these PTs). Adverse events reporting any of these terms will be medically reviewed on a regular basis throughout the duration of the study and will be summarized in the study CSR.

Adverse Event Severity and Relationship to Study Drug

The investigators will rate the severity of each AE as mild, moderate, or severe.

The investigator will use the following definitions to rate the severity of each AE:

Mild	The AE is transient and easily tolerated by the subject.
Moderate	The AE causes the subject discomfort and interrupts the subject's usual activities.
Severe	The AE causes considerable interference with the subject's usual activities and may be incapacitating or life-threatening.

The investigator will use the following definitions to assess the relationship of the AE to the use of study treatment:

Reasonable Possibility	After consideration of factors including timing of the event, biologic plausibility, clinical judgment, and potential alternative causes, there is sufficient evidence (information) to suggest a causal relationship.
No Reasonable Possibility	After consideration of factors including timing of the event, biologic plausibility, clinical judgment, and potential alternative causes, there is insufficient evidence (information) to suggest a causal relationship.

Pregnancy

If a pregnancy occurs in a study subject, information regarding the pregnancy and the outcome will be collected. While not an AE, pregnancy in a study subject must be reported to AbbVie within 24 hours after the site becomes aware of the pregnancy. Any female subject who becomes pregnant while participating in the study will not be eligible to receive further study intervention but should remain in the study to ensure adequate follow-up of safety and efficacy data through the end of the respective treatment cycle, and then be exited from the study.

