10.2.2 Adverse Event Overview

An overview of AEs will be presented consisting of the number and percentage of subjects experiencing at least one event for each of the following AE categories:

- Any treatment-emergent AE
- Any treatment-emergent AE related to study treatment according to the investigator
- Any severe treatment-emergent AE
- Any serious treatment-emergent AE
- Any treatment-emergent AE related to distant spread of toxin
- Any treatment-emergent AE leading to discontinuation of study treatment
- Any treatment-emergent AE leading to death
- Any treatment-emergent AE related to COVID-19
- All deaths

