10.7 Safety Subgroup Analyses

The analysis of treatment-related TEAEs (by descending order of PT incidence) will be repeated for subgroups defined by each randomization stratification group (monthly migraine days at baseline \geq [yes/no] and [redacted]
[redacted] [yes/no]), for medication overuse subgroup [yes/no] (see Section 8.2 in the Operations Manual), for each gender, for each country, for age [< 40 , ≥ 40], and for each race.

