14.1 Changes to Planned Analyses in the Protocol

Three new endpoints were added to SAP Section [3.3](#) listed as below and corresponding analyses were added to Section [9.5.7](#).

- Responder status of at least █-point improvement (increase) in MSQ v2.1 RFR score at Month 6
- Responder status of at least █-point improvement (increase) in MSQ v2.1 RFR score at Month 6
- Responder status of at least █-point improvement (decrease) in AIM-D PI score across Months 5 and 6

The efficacy subgroup analyses for age [$< 40, \geq 40$], for each race, and for prophylactic treatment failure subgroup [failed fewer than █ preventive treatments or failed at least █ preventive treatments] for the primary efficacy endpoint were added in SAP Section [9.7](#).

The safety subgroup analyses for age [$< 40, \geq 40$] and for each race for treatment-related TEAEs were added in SAP Section [10.7](#).

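### The planned safety subgroup tables show only adverse events the investigator judged treatment-related; no all-causality TEAE table is planned for any subgroup

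*Protocol*

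**What the plan says.** Protocol 7.5, in its closing part on subgroups, names one analysis: "The analysis of treatment-related TEAEs (by descending order of PT incidence) will be repeated for subgroups defined by each randomization stratification group". The other factors are medication overuse, gender and country. It then defers anything further: "Additional subgroup analyses will be described in the SAP".

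SAP 10.7 uses the same starting point, "The analysis of treatment-related TEAEs (by descending order of PT incidence) will be repeated for subgroups", and adds age (below 40, or 40 and over) and race as factors. It adds no further endpoint. SAP 14.1 confirms this for the new factors: "and for each race for treatment-related TEAEs were added in SAP Section". The deferral in the Protocol therefore does not widen the scope.

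Relatedness is the investigator's call. The SAP 10.2.2 overview counts "Any treatment-emergent AE related to study treatment according to the investigator". Protocol 6.1 offers two categories, and an event goes into the unrelated one when "there is insufficient evidence (information) to suggest a causal relationship".

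For the whole population the plan is not restricted in this way. Protocol 7.5 and SAP 10.2.3 tabulate all TEAEs by arm, including a listing of preferred terms in descending order of frequency.

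**The concern.** A safety subgroup table is meant to show whether some kind of subject has more of some event on BOTOX than on placebo. Here the events pass through a filter first: someone must have judged them related to treatment. That judgement is made after treatment and with incomplete information, and its default is unrelated when evidence is insufficient.

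Two consequences follow. First, events are discarded. An excess among, say, subjects aged 40 or over that investigators put down to background illness would appear in no planned subgroup table. This needs no unblinding; equal attribution in all arms is enough. Second, the comparison is open to differential attribution, because the opinion may vary with the treatment the investigator believes was given. Between countries, which are one of the listed factors, it may also vary with local habits of attribution.

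The sponsor does not rely on the filter for the whole population. Neither document says why the subgroup tables should.

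**Working it through.** **Step 1. Which outputs are planned by subgroup.**

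| Safety output | By arm | By subgroup |
|---|---|---|
| All TEAEs by preferred term | Protocol 7.5, SAP 10.2.3 | none |
| Treatment-related TEAEs by preferred term | Protocol 7.5, SAP 10.2.3 | Protocol 7.5, SAP 10.7 |
| Serious TEAEs; TEAEs leading to discontinuation | Protocol 7.5, SAP 10.2.4 | none |
| Possible distant spread of toxin (PDSOT) | Protocol 7.5, SAP 10.2.5 | none |
| Laboratory, vital signs, C-SSRS | SAP 10.3 to 10.5 | none |

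All adverse events are also listed by subject (Protocol 7.5, SAP 3.4), but a listing makes no comparison.

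**Step 2. What the planned subgroup table would show of a true excess.** The documents give no TEAE rates or attribution shares, so these values are assumptions. Let D be the true excess on BOTOX within the subgroup, in percentage points, and r the share of events judged related, equal in both arms, with one such event per affected subject. The table shows r × D.

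- D = 10 (10% v 20%), r = 0, 0.1, 0.3, 0.5: 0, 1, 3, 5 points.
- D = 4 (4% v 8%, closer to the scale of single preferred terms): 0, 0.4, 1.2, 2.0 points.

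**Step 3. What the all-TEAE table by arm would show.** Let f be the subgroup's share of each arm, with the excess confined to that subgroup. The arm-level table shows f × D.

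- D = 10, f = 0.15, 0.33, 0.50: 1.5, 3.3, 5.0 points.
- D = 4: 0.6, 1.3, 2.0 points.

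The excess is still counted, but it is diluted and not linked to the subgroup.

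**Step 4. How far visible toxin effects could distort attribution in the double-blind phase.** Protocol 2.2 gives 3.6% for eyelid ptosis and 2.2% for facial paresis in the Phase 3 chronic migraine studies. Per arm of 259 (Protocol 7.8): 259 × 0.036 = 9.3 and 259 × 0.022 = 5.7, so at most about 15 subjects (5.8%) if the two do not overlap.

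Assume equal true TEAE rates T in both arms, 20% of events judged related as background, and, as an extreme, every other event in the visibly affected fraction u re-attributed to treatment. The false excess is T × u × (1 − 0.20).

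- Low end: 0.10 × 0.036 × 0.80 = 0.29 points.
- High end: 0.50 × 0.058 × 0.80 = 2.32 points.

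Counting muscular weakness (3.5%) as visible too gives u = 0.036 + 0.022 + 0.035 = 0.093 and raises the high end to 0.50 × 0.093 × 0.80 = 3.7 points. These totals would be spread over many preferred terms, so any single row would move less.

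**Step 5. The open-label phase.** SAP 10.1 applies the Section 10 methods, unless stated otherwise, to four cases: double-blind phase, open-label phase, whole post-injection period and each treatment cycle. Section 10.7 falls under that rule. In the open-label phase every treated subject receives BOTOX 195 U and the investigator knows it. Relatedness is then judged in full knowledge of treatment and without a concurrent placebo arm.

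**The case against.** The best defence is that this is a scope decision. The Protocol heads the section as covering key safety endpoints, picks one table to repeat, and the SAP follows it consistently. Safety output is descriptive; no subgroup safety test or decision rule is specified. Several safeguards exist: identical vials, an independent reconstitutor and 39 injections in every arm (Protocol 5.8); a fixed list of 40 preferred terms for PDSOT that does not depend on the investigator's relatedness call (SAP 10.2.5); all-causality tables by arm; and listings of every event. The safety set is analysed as treated, so even an all-TEAE subgroup comparison is not strictly protected by randomisation. Reporting of subjective events can itself depend on the perceived arm.

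All of this stands, and it rules out three stronger readings that a reader might infer.

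- That an excess judged unrelated vanishes. It does not; it enters the arm-level tables, the PDSOT summary where the term is on that list, and the listings. It is missing only from subgroup tables.
- That visible toxin effects would create a subgroup excess by attribution alone. Ptosis or facial paresis recorded as related is a real drug effect, correctly classified. Only other events in the same subjects could be misattributed, and Step 4 shows that route is small. A larger shift across a whole arm has no support in the documents.
- That subgroup safety conclusions would be wrong. The plan draws no formal conclusions from these tables, so neither an error rate nor a power figure describes anything it intends to do.

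The safeguards do not supply an all-causality view by subgroup, and removing the relatedness filter reduces attribution bias even if it does not end it.

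**Conclusion.** The point holds as a limited gap in scope. Every planned safety subgroup table is restricted to events the investigator judged related, and no planned output shows all-causality TEAEs by subgroup. This rests on the text of both documents and needs no assumption.

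The size depends on unknown rates. In general, the planned table retains the fraction r of a true subgroup excess, and the arm-level table retains the fraction f; both can be well below one half. Distortion from visible toxin effects is probably minor in the double-blind phase: about 0.3 to 2.3 points on the assumptions of Step 4, which borrow chronic migraine rates and an assumed 20% background share. It cannot be sized in the open-label phase. Nothing here touches the efficacy analyses or the arm-level safety comparison. The change is worth making because it is inexpensive.

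**What to change.** In Protocol 7.5 and SAP 10.7, make all TEAEs by preferred term, in descending order of incidence, the main descriptive subgroup safety table for each listed factor. Keep the treatment-related table beside it as supportive, and record the change in SAP 14.1.

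The table format already exists for the arms, the subgroups are already defined, and the events are already collected and coded. SAP 10.7 lists seven factors (two stratification factors, medication overuse, gender, country, age, race), so the cost is seven further tables for each period reported. The downside is longer tables with more background events, and small counts in some country and race groups. No hypothesis test is added, so control of type I error is unaffected.
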